9.5 Design Changes

Following a pre-planned interim analysis of primary endpoint OS, accrual to Step 1 of this study was suspended on February 23, 2015 based on DSMC's recommendation, due to differences in overall survival favoring standard daunorubicin and cytarabine compared to clofarabine for induction and consolidation. By that time, 727 patients had been accrued to this study.

Among those 727 patients, 120 (16.5%) entered the second randomization. The original protocol design requires 172 patients to be randomized to either the decitabine arm or the observation arm (number of DFS events needed 140), in order to have 90% power to detect approximately a 36% reduction in the DFS hazard rate in the decitabine maintenance therapy arm at the significance level of 0.1.

We plan to reopen the study to accrue additional 52 patients to the second randomization, to finish the accrual goal of 172 patients. This requires about 74 CR/CRI Patients to be pre-registered after their induction therapy. Patients will receive consolidation while on study and then will be randomized to receive either decitabine maintenance treatment or observation, stratified on the induction therapy, cytogenetics and age. Based on the accrual rate of the first 120 randomized patients, we anticipate the additional accrual could be completed within 1.8 years. The final analysis will be performed at 2 years of follow-up after the completion of the accrual. Based on the event rate observed, at that time, 125 DFS events could occur. The study will have approximately 90% power to detect a 37% reduction in the DFS hazard rate in the decitabine maintenance therapy arm, using a one-sided log-rank test at the significance level of 0.1. The half width of two-sided 80% confidence interval on the log hazard ratio (decitabine /observation) will be about 0.23. The half width of two-sided 95% confidence interval on the log hazard ratio (decitabine /observation) will be about 0.35.

Prior to the study reopen, as the study has reached 60% information for the maintenance comparison (Arms E vs. F), an interim analysis will be performed and the maintenance randomization will be monitored for early stopping in favor of null hypothesis by computing the conditional power. The conditional power will be calculated given the current data, assuming the study will continue until 125 events of the maintenance comparison is reached. If the conditional power is higher than 0.7, the study will be reopen to pre-register 74 CR/CRI patients and accrue additional 52 patients to the second randomization. The cutoff of conditional power is set high, as we want to reopen the study only if there is a good chance of a positive result.

If the conditional power is lower than 0.7, the study will be closed permanently. No more patients will be accrued. Based on the current event rate of the 120

patients, the events are anticipated to be accumulated very slowly. Therefore, the final analysis of the maintenance comparison will be performed at six months after the interim analysis. Based on the current event rate, at that time, we assume 90 DFS events could be observed. With 90 events, the study will have approximately 85% power to detect a 36% reduction in the DFS hazard rate in the decitabine maintenance therapy arm, using a one-sided log-rank test at the significance level of 0.15. The half width of two-sided 70% confidence interval on the log hazard ratio (decitabine /observation) will be about 0.22. The half width of two-sided 95% confidence interval on the log hazard ratio (decitabine /observation) will be about 0.41.

Rev.2/13

9.6 AML Clinical Epidemiology

We assume that approximately 600 (82% of all 727 registered to Step 1) patients will complete the ALESE questionnaire. The proportions of obese patients and patients who had benzene exposure, ever smoked in their lifetime, took aspirin regularly, took acetaminophen regularly, ever lived in rural/farm environments, or had other exposures or lifestyle factors will be calculated separately, along with their 95% CIs. With 600 patients, the width of the 95% CI will be no wider than 0.08.

We will examine the impact of smoking, obesity, regular acetaminophen use, regular aspirin use, benzene exposure, and living in a rural/farm environment on OS. The impact of some other exposures or lifestyle factors on OS will also be explored. Assume 50% patients ever smoked in lifetime and assume for those patients a 10% long-term cure rate and 8-month median overall survival in the non-cured group. With treatment arms combined, the study will have approximately 80% power to detect a 22% reduction in the hazard rate in non-smoking patients, using a one-sided log rank test at the significance level of 0.025 and assuming 2 years of follow-up. The number of events needed is 502. Assume 20% patients had benzene exposure and assume those patients have a 10% long-term cure rate and 7.5 -month median overall survival in the non-cured group. With treatment arms combined, the study will have approximately 80% power to detect a 27% reduction in the hazard rate in non- benzene- exposure patients, using a one-sided log rank test at the significance level of 0.025 and assuming 2 years of follow-up. The number of events needed is 482. When data are available, a one-sided log-rank test stratified by induction treatment effect will be used to evaluate the impact of those exposures or lifestyle factors on OS. Moreover, the weighted analysis as described in Section [9.2](#) will also be used in order to reduce the potential bias from the maintenance therapy. Patients receiving alloSCT will be included in this analysis.

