We assume that 635 patients (87% of 727 patients) will submit samples and have sufficient material for mutation analysis. We estimate about 20 mutations will be examined. For a mutation with 50% prevalence, we assume for those mutated patients a 10% long-term cure rate and 7.5-month median overall survival in the non-cured group. With treatment arms combined, the study will have approximately 81% power to detect a 29% reduction in the hazard rate in wild-type patients, assuming 2 years of follow-up. The number of events needed is 528. For a mutation with 20% prevalence, we assume those mutated patients have a 10% long-term cure rate and 6.3-month median overall survival in the non-cured group. With treatment arms combined, the study will have approximately 81% power to detect a 35% reduction in the hazard rate in wild-type patients, assuming 2 years of follow-up. The number of events needed is 501. Those power calculations were based on a two-sided log rank test with the family-wise type I error rate controlled at 0.05 using the Bonferroni correction. For each mutation we will perform a stratified log-rank test (using the strata at randomization) adjusted for multiple testing using resampling and the min-p method of Westfall and Young (1993) as implemented in the R package multtest. In addition we will perform tests for interaction between treatment assignment and mutational status to identify potential predictive mutations. We will begin these analyses by assessing the prognostic relevance of known mutations on overall survival and response to therapy, including FLT3, DNMT3A, IDH1, IDH2, TET2, ASXL1, WT1, and MLL, and we will also include novel mutations identified in our discovery studies and by other efforts (including the AML TCGA project) to determine if novel mutations affect outcomes in this cohort of elderly patients with AML.

Rev. 2/12

We will also identify prognostic risk groups by using recursive partitioning and logistic regression, both of which are highly suitable for binary predictors. We plan to use a randomly chosen subsample of 423 (2/3 of 635) patients for training these models and the remaining 212 for validation.

Rev. 2/12

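### Section 9.6 tests six non-randomised exposures on OS stratified only by the randomised induction arm, leaving age, therapy-related AML and AHD unadjusted

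*Combined protocol and SAP*

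**What the plan says.** Section 9.6 expects about 600 completed ALESE questionnaires. It names six exposures for analysis against OS and says that others will be explored. The test specified for their effect on OS is "a one-sided log-rank test stratified by induction treatment effect". Two exposures are powered, each "using a one-sided log rank test at the significance level of 0.025":

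- Smoking ("Assume 50% patients ever smoked in lifetime"): "approximately 80% power to detect a 22% reduction in the hazard rate in non-smoking patients", with 502 events.
- Benzene (20% exposed): "approximately 80% power to detect a 27% reduction in the hazard rate in non- benzene- exposure patients", with 482 events.

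The only other analysis named is the Section 9.2 weighting, whose stated purpose is to reduce bias from maintenance therapy. Section 9.6 gives no covariate adjustment and no multiplicity rule.

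Elsewhere the document handles similar comparisons differently. In Section 9.8: "For each mutation we will perform a stratified log-rank test (using the strata at randomization) adjusted for multiple testing". Section 9.2 uses age, therapy-related AML and AHD as stratification factors for primary OS. Section 9.4 stratifies the non-randomised transplant comparison by the same three factors plus induction therapy.

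**The concern.** Patients are not allocated to smoke, take aspirin or live on a farm, so a difference in survival between exposure groups mixes any exposure effect with differences in prognosis. Stratifying by induction arm does not address this, because randomisation already makes the arm independent of earlier exposures apart from chance.

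The factors that could address it are at hand. Age, therapy-related AML and AHD are stratification factors at the first randomisation (Section 4.2.5). Section 1.6.5 says that therapy-related AML has an inferior outcome. If an exposure is more common among patients who are older or have had a previous cancer treated, the planned test will tend to attribute their worse survival to the exposure. If it is less common among them, a real harmful effect could be hidden.

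A separate matter is direction. Objective 2.2.9 is to examine impact, and Section 1.6.5 says the effect of these factors on survival is unknown. A direction is implied only for smoking and benzene, through their power statements. The incidence associations cited for aspirin (relative risk 0.6 in women) and acetaminophen (1.5) point in opposite directions. An effect in the untested direction could be estimated but not declared.

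**Working it through.** **1. The plan's power figures.** Inputs from Section 9.6: smoking 502 events, hazard ratio (HR) 0.78, split 50/50; benzene 482 events, HR 0.73, split 20/80; one-sided 0.025. Schoenfeld's formula is power = Φ(√(d·p·(1−p))·|ln HR| − z).

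- Smoking: √(502 × 0.25) = 11.20; 11.20 × 0.2485 = 2.783; 2.783 − 1.960 = 0.823; power 79.5%.
- Benzene: √(482 × 0.16) = 8.78; 8.78 × 0.3147 = 2.764; 2.764 − 1.960 = 0.804; power 78.9%.

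Both agree with the stated figure of about 80%.

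**2. Two-sided testing.** One-sided 0.025 and two-sided 0.05 share the critical value 1.960, so power stays at 79.5% and 78.9%.

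**3. Adjustment factors by analysis.**

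| Analysis | Factors used |
|---|---|
| Primary OS (9.2), randomised | age, therapy-related AML, AHD |
| Transplant OS (9.4), not randomised | age, therapy-related AML, AHD, induction therapy |
| Mutations (9.8), not randomised | randomisation strata |
| CXCR4 (9.8), not randomised | treatment and prognostic factors including cytogenetics |
| ALESE exposures (9.6), not randomised | induction treatment only |

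**4. Illustrative size of confounding.** The documents give no association between any named exposure and age, therapy-related AML or AHD, so every input here is an assumption: confounder HR 1.4, prevalence 40% in the unexposed and 55% to 65% in the exposed, no true exposure effect. The spurious HR is approximately the ratio of average hazards:

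- 15 points: (1 + 0.4 × 0.55)/(1 + 0.4 × 0.40) = 1.22/1.16 = 1.05.
- 25 points: (1 + 0.4 × 0.65)/(1 + 0.4 × 0.40) = 1.26/1.16 = 1.09.

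On the z scale, smoking shifts by 11.20 × ln(1.22/1.16) = 0.57 to 11.20 × ln(1.26/1.16) = 0.93. The chance of a false positive in the tested direction rises from 2.5% to 1 − Φ(1.960 − 0.57) ≈ 8%, up to 1 − Φ(1.960 − 0.93) ≈ 15%.

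A fuller large-sample log-rank calculation, with an assumed 9-month median and 10% cured, gives the range under other assumptions for the smoking comparison:

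| Prevalence, exposed vs unexposed | Confounder HR | Apparent HR | False-positive rate |
|---|---|---|---|
| 50% vs 40% | 1.3 to 2.0 | 1.03 to 1.07 | 4.7% to 10.6% |
| 60% vs 40% | 1.3 to 2.0 | 1.05 to 1.14 | 8.4% to 30.5% |
| 30% vs 10% | 1.5 to 2.0 | 1.08 to 1.13 | 13% to 26% |

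**5. Multiplicity.** Six independent tests at one-sided 0.025 give 1 − 0.975⁶ = 0.141. Bonferroni uses 0.025/6 = 0.00417 (z = 2.638). Power becomes Φ(2.783 − 2.638) = 55.8% for smoking and Φ(2.764 − 2.638) = 55.0% for benzene. Restoring 80% would need 785 and 765 events, more than the 600 expected respondents.

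**The case against.** Four points can be made for the plan.

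*A fuller plan is promised.* Section 1.6.5 defers a detailed analysis plan, including clinical and cytogenetic data, to a grant application. So Section 9.6 may not be the last word. But the deferral commits to no adjustment set, and Section 9.6 is the only test specified.

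*The weighted analysis may carry the strata.* Section 9.2 attaches age, therapy-related AML and AHD to its weighted OS analysis, and Section 9.6 cites that analysis. Section 9.6 cites it only to deal with maintenance therapy, however, and does not say that the strata come with it. The log-rank test plainly lacks them.

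*Adjustment can itself mislead.* This stands. Section 1.6.5 links smoking to t(8;21), so cytogenetics may lie on the path from exposure to survival. Therapy-related AML and AHD may do so too. A single fully adjusted model would then estimate a direct effect rather than the total effect. Age is not open to this objection.

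*Multiplicity control is not free.* This also stands. The six exposures are separate, pre-named questions within one secondary objective, and formal control would cost about 24 points of power. The CXCR4 analysis in Section 9.8 has no multiplicity rule either.

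A reader might infer that one-sided testing and the lack of multiplicity control make the confounding worse. They do not: confounding comes from the missing adjustment alone. One-sided 0.025 does not inflate error in a pre-stated direction.

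**Conclusion.** The gap is real and narrow. Followed as written, the Section 9.6 log-rank test leaves confounding by age in place, and possibly by therapy-related AML and AHD, for six observational exposures. The document's own practice in Sections 9.2, 9.4 and 9.8 supplies the remedy.

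The size is unknown. A spurious HR of 1.05 to 1.09 is an illustration resting on an assumed confounder HR of 1.4, 40% baseline prevalence and a 15 to 25 point imbalance. It is smaller than the effects the section is powered for (1/0.78 = 1.28 and 1/0.73 = 1.37), though enough to raise the false-positive rate if imbalances of that order exist. A reader might infer that the exposure results are known to be biased by this amount; no section shows that any named exposure tracks with age.

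A reader might also infer that the 14% family-wise error requires formal correction. The documents do not compel that; labelling the results hypothesis-generating is enough. The stated power calculations are sound. Only objective 2.2.9 is affected, not the primary OS comparison.

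**What to change.** Amend Section 9.6 as follows.

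1. Test each named exposure two-sided at 0.05, with a log-rank or Cox analysis stratified by induction arm and the randomisation strata (age, therapy-related AML, AHD).
2. Report beside it a model adjusted for age only, because therapy-related AML and AHD may be on the causal path. Treat any cytogenetics-adjusted model as a sensitivity analysis.
3. State that the six exposure results are hypothesis-generating, and give the family-wise error of about 14% under independence. Formal control, such as the Section 9.8 resampling method, is optional. If it is adopted, the power statements must be revised; Bonferroni would leave about 55%.
4. Say whether the weighted analysis uses the same strata.

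The cost of items 1, 2 and 4 is wording: the strata are recorded at randomisation, and two-sided testing leaves the power calculation unchanged. Treating the three factors as binary, stratification gives 2 × 2 × 2 × 2 = 16 cells, averaging 600/16 = 37.5 respondents. If some cells prove too thin, the same factors can enter the Cox model as covariates.

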9.7 Quality of Life

9.7.1 Primary Endpoint

Quality of life (QOL) will be assessed using the FACT-Leukemia and FACIT Fatigue instruments as well as the Geriatric Assessment Battery. The FACT-Leukemia and FACIT –Fatigue instruments will be administered at the following time points: at the time of randomization, two weeks after beginning induction therapy (at the time of nadir), at 28 – 30 days after beginning induction therapy, at the time of beginning consolidation therapy, at the time of randomization to

maintenance therapy or observation, and also at the time the patient discontinues treatment. The Geriatric Assessment Battery will be administered at the time of induction randomization for a baseline assessment. The primary objective of the QOL study is to compare health-related QOL in elderly AML patients receiving standard induction therapy with those receiving clofarabine. Of primary interest are the scores on the FACT-Leu TOI (combines Physical Well-Being + Functional Well-Being components of FACT-G and leukemia-specific subscales) and FACIT Fatigue score. The FACT-Leu TOI has 31 items and the score ranges from 0-124. The FACIT Fatigue has 13 items and the score ranges from 0-52. The primary endpoints will be defined as the change of the FACT-Leu TOI score and change of FACIT Fatigue scores from time of randomization to day 28 – 30 after beginning induction therapy. The changes of the FACT-Leu TOI score and changes of FACIT Fatigue scores will both be tested at a nominal level of 0.025 (two-sided) to adjust for multiple comparisons.

The FACT-Leu TOI is reported to have a standard deviation (SD) ranging from 18.1-21.7. Differences in FACT-Leu TOI mean change scores between the standard treatment arm and the clofarabine arm from time of randomization to day 28 – 30 after beginning induction therapy that can be detected with 80% power at two-sided significance level of 0.025 are presented in the following table. The expected survival models for each treatment arm specified in Section [9.2](#) were used to establish the estimated number of patients alive at day 28 – 30 after beginning induction therapy. A sensitivity analysis for the % of patients assumed alive to complete the questionnaire at day 28 – 30 after beginning induction therapy (65%, 80%), allowing for slightly less and more variability in the instrument (18.0, 20.0, 22.0) and assuming different correlation (0.4, 0.6) between repeated measures was performed. For example, assuming a SD of 22.0 for the FACT-Leu TOI, a correlation between repeated measures of 0.6 and using a two-sided t-test with a 0.025 significance level, there is sufficient power to detect a true difference in the FACT-Leu TOI mean change score between the two arms of 5.1-5.7.

Table 2: Differences in FACT-Leu TOI Mean Change Scores

Standard deviation (SD)	Correlation	SD of change	Difference between treatment arms in mean change score from time of randomization to day 28 – 30 after beginning induction	
			65% compliance (n=456)	80% compliance (n=561)
18.0	0.4	19.7	5.7	5.1
	0.6	16.1	4.7	4.2
20.0	0.4	21.9	6.3	5.7
	0.6	17.9	5.2	4.7
22.0	0.4	24.1	7.0	6.3
	0.6	19.7	5.7	5.1

The FACIT Fatigue scores are reported to have a standard deviation (SD) ranging from 9.4-13.6. Differences in FACIT Fatigue mean

change scores between the treatment arms from time of randomization to day 28 – 30 after beginning induction therapy that can be detected with 80% power at two-sided significance level of 0.025 are presented in following table. For example, assuming a SD of 12.5 for the FACIT Fatigue, a correlation between repeated measures of 0.6 and using a two-sided t-test with a 0.025 significance level, there is sufficient power to detect a true difference in the FACIT Fatigue mean change score between the two arms of 2.9-3.2.

Table 3: Differences in FACIT Fatigue Mean Change Scores

Standard deviation (SD)	Correlation	SD of change	Difference between treatment arms in mean change score from time of randomization to day 28 – 30 after beginning induction	
			65% compliance (n=456)	80% compliance (n=561)
9.5	0.4	10.4	3.0	2.7
	0.6	8.5	2.5	2.2
11.0	0.4	12.0	3.5	3.1
	0.6	9.8	2.8	2.6
12.5	0.4	13.7	4.0	3.6
	0.6	11.2	3.2	2.9
14.0	0.4	15.3	4.4	4.0
	0.6	12.5	3.6	3.3

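### The primary quality-of-life test is a t-test on raw change scores; adjusting the follow-up score for baseline would cut the variance by 20–30% under the plan's own assumptions, with no new data.

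*Combined protocol and SAP*

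**What the plan says.** Section 9.7.1 sets the endpoints: "The primary endpoints will be defined as the change of the FACT-Leu TOI score and change of FACIT Fatigue scores from time of randomization". The follow-up time point is day 28–30 after induction begins. Both changes "will both be tested at a nominal level of 0.025 (two-sided) to adjust for multiple comparisons". The differences in Tables 2 and 3 are those that "can be detected with 80% power at two-sided significance level of 0.025". The tables use a single SD per row (18.0, 20.0 or 22.0 for TOI; 9.5 to 14.0 for FACIT Fatigue), and the text states that a sensitivity analysis "assuming different correlation (0.4, 0.6) between repeated measures was performed". Total sample sizes are 456 at 65% compliance and 561 at 80%.

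The only test named for these endpoints is in the worked examples: "using a two-sided t-test with a 0.025 significance level". Section 9.7.1 mentions neither the baseline score as a covariate nor the Step 1 stratification factors (age group, therapy-related AML, antecedent hematologic disorder). Section 9.7.2 adds a repeated-measures model fitted jointly with time to dropout, as a secondary analysis. Section 6.7 already schedules the baseline questionnaire as T1, before induction.

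**The concern.** Subtracting the baseline forces its coefficient to be 1. When the correlation between the two measurements is moderate, that over-corrects and adds noise from the baseline measurement. Table 2 shows this: with SD 18.0 and correlation 0.4, the SD of change is 19.7, larger than the SD of the score itself. The SD of change exceeds the raw SD whenever r is below 0.5, so it does in all seven r=0.4 rows of Tables 2 and 3. In half of the planning scenarios the analysis is therefore less precise than one that ignored the baseline.

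What is at stake is precision on the two comparisons that carry the quality-of-life objective. Section 9.5 records that Step 1 accrual stopped at 727 patients, against 747 planned, and the proposed reopening concerns only the maintenance randomization. More induction patients are not available, so a more efficient analysis is the remaining way to gain precision. The t-test also leaves out the randomization strata, although the OS, DFS and transplant analyses in Sections 9.2 and 9.4 are all stratified.

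**Working it through.** **Inputs (Section 9.7.1).** Two-sided alpha 0.025 per scale; power 80%; r = 0.4 or 0.6; one SD for both times; N = 456 or 561 in total. Equal allocation is assumed.

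**Step 1: reproduce the plan.**

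- SD of change = SD × √(2(1−r)).
- Detectable difference = (2.2414 + 0.8416) × SD of change × √(4/N). The multiplier of the SD is 3.083 × √(4/456) = 0.2887 for N=456, and 3.083 × √(4/561) = 0.2603 for N=561.
- For SD 22 and r=0.6: SD of change = 22 × √0.8 = 19.7. The detectable difference is 5.7 (N=456) and 5.1 (N=561), as the plan states.

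All 14 rows of Tables 2 and 3 reproduce to within 0.05 point, and power at the stated differences is 79.1–81.6%. The Ns also reproduce: 747 times the mean survival at day 30 under the Section 9.2 models is about 701; 65% of that is 456 and 80% is 561.

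**Step 2: adjust for baseline instead.** Under randomization both analyses estimate the same difference between arms, so their variances can be compared directly.

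- Change score: 2(1−r) × SD².
- Follow-up score adjusted for baseline: (1−r²) × SD².
- Ratio: (1−r²) / [2(1−r)] = (1+r)/2, which is 0.70 at r=0.4 and 0.80 at r=0.6.

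The change-score analysis would need 1/0.70 = 1.43 or 1/0.80 = 1.25 times as many patients for the same precision. Detectable differences shrink by 1−√0.70 = 16% or 1−√0.80 = 11%.

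**Step 3: results for TOI with SD 20.**

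| r | SD of change | Adjusted SD | N=456: change → adjusted | N=561: change → adjusted |
|---|---|---|---|---|
| 0.4 | 21.9 | 18.3 | 6.3 → 5.3 | 5.7 → 4.8 |
| 0.6 | 17.9 | 16.0 | 5.2 → 4.6 | 4.7 → 4.2 |

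For the plan's TOI example (SD 22, r=0.6) the detectable difference falls from 5.7 to 5.1 (N=456) and from 5.1 to 4.6 (N=561). For its FACIT Fatigue example (SD 12.5, r=0.6) it falls from 3.2 to 2.9 and from 2.9 to 2.6. Across all rows, power at the plan's stated differences rises to about 92–93% (r=0.4) or 88–90% (r=0.6).

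**Step 4: simulation check.** With SD 22, 228 patients per arm and 4,000 runs per correlation, the variance ratios were 0.706 and 0.796. Power rose from 80.5% to 92.7% (r=0.4, difference 7.0) and from 79.9% to 88.4% (r=0.6, difference 5.7).

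**Step 5: unequal SDs.** If the follow-up SD is k times the baseline SD, the ratio is k²(1−r²) / (1 + k² − 2rk). The denominator minus the numerator equals (1−rk)², which is never negative, so in large samples the adjusted analysis is never the less precise one. At k=1.2 (an assumption; the documents give no SDs by time point) the ratio is 0.82 at r=0.4 and 0.92 at r=0.6, a cut of about 18% or 8%.

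**The case against.** The strongest reply is that the t-test appears only in a power example, and that elsewhere the plan powers on a simple test and analyses with an adjusted one. It does this for DFS and the transplant comparison in Section 9.4 and for CXCR4 in Section 9.8. In each of those places, however, the adjusted final analysis is written down. Section 9.7.1 writes down none, so the t-test on change is the only analysis on record.

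Second, nothing is invalid: a t-test on change is unbiased under randomization and its 80% power is right. This stands, and it makes the point one of efficiency. Third, the joint model in Section 9.7.2 already uses the baseline score. It does, but as a secondary analysis that does not replace the primary test.

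Fourth, the size of the gain depends on equal SDs, and at r=0.6 it is only about 0.5–0.6 point on a 0–124 scale. Both statements are correct, and the gain from the stratification factors cannot be quantified from the documents. Fifth, Step 1 accrual is over, so the tables can no longer guide sample size, and changing a primary quality-of-life analysis late carries a credibility cost. That is a condition on when to make the change; it does not remove the gain.

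Finally, adjustment among completers does not solve missing data from death or non-completion. Nor does it resolve the mismatch between day 28–30 in Section 9.7.1 and the day 35–56 assessment in Sections 6.7 and 7.1. Both need attention whichever test is used.

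**Conclusion.** The concern holds. Under the plan's own planning values, baseline adjustment would reduce the variance of both primary quality-of-life comparisons by 30% (r=0.4) or 20% (r=0.6). This rests on equal SDs at the two times, on the stated correlations and on large-sample behaviour. With unequal SDs the gain can be smaller, but the adjusted analysis is still no worse. It is an improvement that should be made, not the correction of an error.

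**What to change.** In Section 9.7.1, replace the t-test with a linear model of the follow-up score at the primary time point on arm, baseline score and the three Step 1 stratification factors, tested at two-sided 0.025 for each scale. Recompute Tables 2 and 3 with SD × √(1−r²) in place of the SD of change, and state the equal-SD assumption. Keep the Section 9.7.2 joint model for informative dropout.

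The cost is SAP wording. A change score already requires the baseline, so no patient is lost and no data are added. The model uses four further degrees of freedom (one for baseline, three for the binary factors) out of more than 450. The documents do not say whether quality-of-life data have been analysed. The amendment should therefore be dated and finalized before anyone sees results by arm; if results have already been seen, report the adjusted model as supportive.
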